# NIH Stroke Scale (NIHSS) measured before the start of mechanical thrombectomy and 24 hours after the procedure.

NIHSS will be assessed at the following time points by a member of the research team:

- any time point after admission to hospital but before induction of anaesthesia
- 24 hours from start of mechanical thrombectomy

Clinically recorded arrhythmias within the first 24 hours after the start of mechanical thrombectomy Defined as electrocardiograph evidence for cardiac rhythm as determined by the treating clinician either documented in the medical records and/ or recorded by a 12 lead ECG.

Absolute levels of serum high-sensitivity troponin-T levels measured before the start of the first transcutaneous autonomic neuromodulation and at the end of the second transcutaneous autonomic neuromodulation.

Additional blood samples to routine care will be collected to measure serum high sensitivity troponin-T (Elecsys, Roche Diagnostics) levels. Blood samples will be collected at any time after hospital admission but before the induction of anaesthesia and within two hours upon the completion of the second transcutaneous autonomic neuromodulation. The time of completion for transcutaneous autonomic neuromodulation is defined as when the device is switched 'on' and 'off' by a member of the research team. If blood samples are not collected, a protocol deviation will be recorded and data point classified as 'missing'.

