	 Exclusion criteria participation in a trial exploring similar biological mechanism; previous enrolment; anatomical contraindication (local ear abnormalities); pregnancy.
Interventions	Active stimulation bilateral active transauricular nerve stimulation for the duration of the mechanical thrombectomy procedure (AffeX-CT/001 investigational device). The intervention will be repeated for 1h the morning following the mechanical thrombectomy
	Sham stimulation bilateral sham transauricular nerve stimulation for the duration of the mechanical thrombectomy procedure (AffeX-CT/001 investigational device). The intervention will be repeated for 1h the morning following the mechanical thrombectomy
Primary outcome measure	The primary outcome is Blood pressure variability [Time Frame: 0-24h after mechanical thrombectomy], as calculated from the coefficient of variation of systolic blood pressure

3. Outcome measures

Primary outcome measure

The primary outcome is Blood pressure variability [Time Frame: 0-24h after mechanical thrombectomy], as reflected by the coefficient of variation of systolic blood pressure.

Secondary outcome measures

- 1. Systolic and diastolic blood pressure variability in the first 24h after mechanical thrombectomy [Time Frame: 0-24h after mechanical thrombectomy]: systolic and diastolic blood pressure mean, standard deviation, and coefficient of variation.
- 2. Heart rate variability [Time Frame: 0-24h after mechanical thrombectomy]: time and frequency domain measures of autonomic cardiac modulation.
- 3. NIH Stroke Scale (NIHSS) [Time Frame: recorded before, at 24h after mechanical thrombectomy]
- 4. Organ dysfunction [Time Frame: First seven days after mechanical thrombectomy.] defined as clinical need for intravenous pharmacological support for blood pressure [pressors or intravenous antihypertensive medication]; arrythmias; myocardial injury [high sensitivity troponin]; hospital-acquired infection.

Exposure variables

The exposure is bilateral active or sham transauricular nerve stimulation for the duration of the mechanical thrombectomy procedure (AffeX-CT/001 investigational device), an intervention that is be repeated for 1h the morning following the mechanical thrombectomy (provided the patient remains in Royal London Hospital).

Sample size and randomisation

Sample size calculation

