 BPV formulae are provided in supplementary data. These measures take into account the distribution and linear trends of BP in an effort to reduce the dependency of BPV on mean BP level.
- 2. Autonomic cardiac modulation in the first 24h after mechanical thrombectomy (Holter monitoring).
- 3. Neurological recovery will be reported by recording serial NIH Stroke Scale (NIHSS) scores, an FDA-approved primary outcome measure for stroke in early phase II trials before and 24h after mechanical thrombectomy.[8]

Exploratory objectives

Biomarkers for risk of infection (whole blood leukocyte transcriptomic changes after incubation at 37°C with sterile saline or 100ng/ml lipopolysaccharide for 4h), infections within 7 days of MT and myocardial injury (high-sensitivity troponin) will also be quantified. Cardiac injury will be assessed by measuring high-sensitivity troponin T on admission and 24h after MT.

Sensitivity analysis

For patients discharged before the repeat stimulation intervention or repatriated to referring centres before the repeat intervention, we will undertake a sensitivity analysis. The primary analysis will be repeated once assuming that all patients in the continue group with missing outcomes did not have BPV >20. The analysis will then be repeated again with the opposite assumptions. This will then give the absolute range of how much the results could change if the data were complete. This will also assess the robustness of our analysis of the primary outcome under the assumption that data is missing-not-at-random (MNAR).

5. Other analyses, data summaries and graphs

Clinical management

Clinical management for the treatment allocation will be summarised but not subjected to statistical testing. Numbers (%) and means (SD) or medians (IQR) will be provided separately for each principal exposure group:

- Thrombectomy technique
- General Anaesthesia/ Sedation
- Endotracheal tube inserted?
- Did the patient have any arrhythmias
- Intraoperative hypotension
- Planned level of care.

Process measures

Summary measures will be presented separately for each treatment allocation. All patients with recorded data will be included in the summary. Formal statistical analysis will not be performed. Patient status at follow up (alive/dead; home/hospital) seven days after MT will be presented as number (%).

Safety analyses

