Appendix 1: Derived outcomes and variables

Primary outcome

CV systolic blood pressure:
$$CV = \left(\frac{SD}{BP_{mean}}\right) * 100$$

Secondary outcomes

For both systolic BP (SBP) and diastolic BP (DBP), the following indices of blood pressure variability will be calculated:

1. Standard deviation SBP/DBP in the first 24h after mechanical thrombectomy.

$$SD = \sqrt{\frac{1}{(n-1)}\sum_{(i=1)}^{(n)} (BP_i - BP_{mean})^2}$$

2. Average real variability in the first 24h after mechanical thrombectomy.

$$ARV = \frac{1}{\sum_{k}^{w_k} \sum_{k=2}^{n} w_k \times |BP_k - BP_{k-1}|}$$

3. Successive variation in the first 24h after mechanical thrombectomy.

$$SV = \sqrt{(1/(n-1))\sum_{(i=1)}^{(n-1)} (BP_{i+1} - BP_i)^2)}$$

4. Residual standard deviation in the first 24h after mechanical thrombectomy.

$$rSD = \sqrt{\frac{\sum (BP - BPest)^2}{n - 2}}$$

Heart rate variability, time domain measures

RR-interval, SDNN, RMSSD, SD HR, NN, pNN

Frequency domain measures

VLF power, VLF peak, LF power, LF peak, HF power, HF peak, DFA1, DFA2.

Peak level of Troponin-T measured within 24 hours of MT

This is defined as the highest troponin-t value measured within 24 hours of mtwhich is collected on admission and 24h post MT [if applicable]. If only one troponin-T value is available, then this will be used as the peak. If troponin-T data is missing for both timepoints, then the outcome will be set to missing.

Infection up to 7 days after mechanical thrombectomy

This is defined as one or more of the following infections (definitions of each type of infection are the same used in the SPACE protocol):

- Superficial surgical site infection
- Deep surgical site infection
- Organ space surgical site infection
- Urinary tract infection
- Infection, source uncertain
- Laboratory confirmed blood stream infection

Equal to 1 if:

- At least one of the components of infection is listed as occurring Equal to 0 if:
- All of the components of postoperative infection are "None"

Missing if:

- All components are missing
- OR one or more of the components of postoperative infection is missing and all other components are "None"

Death and location 7 days after mechanical thrombectomy

Equal to 1 if:

• Patient status at 7-day follow-up is dead/in hospital

[figure not shown]
Equal to 0 if:

• Patient status at 7-day follow-up is alive / out of hospital

Missing if:

- Patient status at 30-day follow-up is missing

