HF, power				
HF, peak				
DFA1				
DFA2				

Table 6. Process/ exploratory measures.

	ACTIVE	SHAM
NIH Stroke Scale (NIHSS) 24h after mechanical thrombectomy (delta change from admission)		
Health status 7 days after mechanical thrombectomy.		
Alive		
Troponin change from admission (delta change from admission)		

Table 7:Adverse events

Adverse Events - no. (%)	active	sham
Patients with ≥ 1 adverse event		
Total number of adverse events		
Type of adverse event		
Cardiac arrythmia		
Local skin irritation		
Other

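### The SAP's troponin peak lets a sample taken before treatment stand as the outcome, and the timing of the second sample is not reconciled with the protocol

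*SAP*

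**What the plan says.** **Protocol.** Section 2.3.2 makes the endpoint the absolute troponin-T levels before the first stimulation and at the end of the second. Appendix A takes the first sample at any point between admission and induction, and the second "within two hours upon the completion of the second transcutaneous autonomic neuromodulation". If a sample is not taken, "a protocol deviation will be recorded and data point classified as" missing. Section 14.6 rules out imputation and analyses complete cases. Section 6.7 sets session 2 for the next morning, typically 08:00 to 12:00, for one hour give or take 10 minutes, whatever the hour of the thrombectomy. The schedule in section 6.2 and the data list in section 6.6 nevertheless file the second sample under a 24-hour heading.

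**SAP.** Section 4 gives the timing as "high-sensitivity troponin T on admission and 24h after MT". Appendix 1 defines the peak: "This is defined as the highest troponin-t value measured within 24 hours of" thrombectomy, drawn from the admission sample and, where there is one, the 24-hour sample. It adds: "If only one troponin-T value is available, then this will be used as the peak". The outcome is missing only if both values are missing. Section 3 gives the repeat session "provided the patient remains in Royal London Hospital", and the sensitivity analysis in section 4 provides for patients discharged or repatriated before it. Table 6 in Appendix 3 reports a third quantity, the change from admission.

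**The concern.** An outcome should be measured after treatment starts. The admission sample precedes any stimulation, so it cannot carry a treatment effect. Under the SAP's rule it can still enter the comparison as a patient's result, which pulls the estimated difference between arms toward zero. The SAP itself expects some patients to leave before session 2, the event to which the protocol ties the second sample.

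The documents also hold three troponin summaries (two absolute levels, a peak, a change) and two descriptions of when the second sample is taken. The analyst would have to choose among them with the data in hand, which the SAP's own remit says it exists to avoid.

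**Working it through.** The plan gives no figure for the share of patients affected, so there is none to reproduce.

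**Step 1: what each document returns.** Let X1 be the pre-induction value and X2 the value after session 2.

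| Samples available | SAP Appendix 1 peak | Protocol |
|---|---|---|
| Both, X2 at least X1 | X2 | X1 and X2 as levels |
| Both, X1 higher | X1 (pre-treatment) | X1 and X2 as levels |
| X1 only | X1 (pre-treatment) | X2 missing |
| X2 only | X2 | X1 missing |
| Neither | missing | both missing |

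Rows two and three put a pre-treatment value in the outcome. Neither depends on start times or on how the 24-hour limit is read.

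**Step 2: dilution from lone admission values.** Suppose a share m of each arm has only X1, the loss is unrelated to outcome, and X1 has the same expectation in both arms. If the arm difference among the remaining patients is D, the expected overall difference is m × 0 + (1 − m) × D = (1 − m)D. With 36 patients randomised 1:1 there are 36/2 = 18 per arm, so one such patient in each arm gives m = 1/18 = 5.6%. The documents do not say how many there will be. Row two dilutes as well, but by an amount that depends on the troponin distributions, which are not given.

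**Step 3: when the second sample falls.** Let t be the clock time at which thrombectomy starts and s the clock time of the second sample next day. From protocol section 6.7 and Appendix A:

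- earliest s = 08:00 + 50 min = 08:50
- latest s = 12:00 + 70 min + 2 h = 15:10 (the widest reading, with the session starting at noon)
- elapsed hours = 24 + s − t

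| Start t | Elapsed, s = 08:50 | Elapsed, s = 15:10 |
|---|---|---|
| 00:00 | 32.8 h | 39.2 h |
| 06:00 | 26.8 h | 33.2 h |
| 10:00 | 22.8 h | 29.2 h |
| 14:00 | 18.8 h | 25.2 h |
| 18:00 | 14.8 h | 21.2 h |
| 24:00 | 8.8 h | 15.2 h |

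The sample therefore falls about 9 to 39 hours after the start.

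**Step 4: the 24-hour limit read strictly.** The sample is outside 24 hours when t is earlier than s. If starts are uniform between clock times a and b, the share outside is (s − a)/(b − a), kept between 0 and 1. The start times are assumptions, because the documents give none.

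| Assumed starts | s = 08:50 | s = 12:00 | s = 15:10 |
|---|---|---|---|
| 00:00–24:00 | 37% | 12/24 = 50% | 63% |
| 08:00–18:00 | 8% | 4/10 = 40% | 72% |
| 12:00–24:00 | 0% | 0% | 26% |
| 18:00–24:00 | 0% | 0% | 0% |
| 00:00–08:00 | 100% | 100% | 100% |

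Counting from the end of a two-hour procedure replaces s by s − 2. With s = 12:00 the first two rows become 10/24 = 42% and 2/10 = 20%. Across these assumptions the share runs from 0% to 100%.

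**The case against.** **The second sample may be safe as the text stands.** A reader might infer that for many patients the second sample falls outside 24 hours and the admission value takes its place. The documents do not support that. Appendix 1 speaks of the "highest troponin-t value measured within 24 hours of mtwhich is collected on admission and 24h post MT", so it names the later sample as eligible, and it then refers to two time points. The protocol files the post-session-2 sample under a 24-hour heading in sections 6.2 and 6.6. Read by visit, no collected sample is lost. The stronger reading needs both a strict cut-off and start times that nobody has stated. This objection stands against any patient count. It does not touch rows two and three of Step 1.

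**The peak may never be reported.** It appears in no dummy table, and Table 6 shows a change. A reader might infer that this change would be exactly zero for patients with one sample. No passage puts the peak into the change, so the change would more naturally be missing. This stands, and it shows that the SAP has not settled which summary it will report.

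**The first sample is not shown to be pre-randomisation.** A reader might assume so, but protocol section 6.1 lists it after randomisation on the day of the procedure. Only pre-treatment is established, and that is enough for the point.

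**The protocol does not say how to form a peak.** It classes the uncollected data point as missing, so the one-sample rule is not a word-for-word contradiction. This stands in part. But complete-case analysis without imputation leaves no room for an admission value to stand in for a later one.

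**The stakes are low.** Protocol section 14.4 lists myocardial injury among the outcomes it will report without testing, and SAP section 4 places troponin under exploratory objectives. This stands and sets the severity. On the other side, SAP section 3 also lists myocardial injury within a secondary outcome, and section 4 promises an effect estimate, interval and p-value for each secondary outcome.

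**Conclusion.** The rule in SAP Appendix 1 is wrong as written. It returns a pre-treatment value as the outcome for any patient with only the first sample, and for any patient whose first value is the higher. This rests on the documents alone. The loss of signal from lone admission values is proportional to their share, about 5.6% for each such patient per arm of 18, under the assumptions in Step 2. Their number is unknown.

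The timing conflict is also real. The protocol fixes the second sample by session 2, about 9 to 39 hours after the start, while the SAP describes a 24-hour sample and a 24-hour limit. Whether any collected sample would be dropped depends on a strict reading and on unstated start times. No count can be given.

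Severity is minor. The primary outcome is unaffected.

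**What to change.** In SAP section 4 (Exploratory objectives) and Appendix 1:

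- Identify the second troponin by protocol visit, as the sample taken after session 2, and report the actual sampling times.
- Replace the peak with the post-session-2 level, reported with its change from the pre-induction sample as in Table 6. This stays within the protocol's endpoint of absolute levels at two times.
- Adjust any between-arm estimate for the first value.
- Delete the one-sample rule and the 24-hour cap. Set the outcome to missing if the second sample is missing. The change is then missing if either sample is.

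The cost is SAP wording and a few more values declared missing. Blood sampling and the visit schedule do not change.

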#### 14.6 Procedure(s) to account for missing or spurious data

As the primary outcome uses routinely captured data stored by Barts Health EPR, there is minimal risk of missing blood pressure-related data. Heart rate data will be captured by dedicated Holter monitors provide by the Chief Investigator. Any missing data will not be inputed. Sensitivity analyses to assess the robustness of study results if there are missing primary outcome data will be undertaken. This pilot study will assess data completeness to inform decisions about missing data for a future main trial. Analysis will use all participants with available endpoint data. The level of missing data will be tabulated for each outcome, presenting the number of subjects with a data record and number with missing data, separately by trial arm. Each endpoint will be analysed on a complete case basis. For continuous variables, distributional assumptions will be hard to assess with the small sample size for this pilot study. However, if any continuous endpoint variables appear to seriously violate distributional assumptions or very extreme outliers observed, then non-parametric alternative approaches to analysis will be undertaken in such cases.

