Baseline characteristics

Baseline characteristics will be summarised for each treatment group by the mean and standard deviation or median and interquartile range for continuous variables, and the number and percent for categorical variables, but not subjected to hypothesis testing. The following baseline characteristics will be summarised by treatment group:

- Demographic: age (years), gender (male/female)
- Co-morbid disease: Chronic obstructive pulmonary disease (COPD), Asthma, Interstitial lung disease or pulmonary fibrosis, Ischaemic heart disease, Congestive heart failure, Diabetes Mellitus, Liver cirrhosis, Active cancer, peripheral vascular disease
- Pre-operative blood test results; Haemoglobin, Creatinine, Neutrophil count, Lymphocyte count, Albumin.
- Cardiovascular medication: Beta-blocker, Calcium channel antagonist (amlodipine/felodipine etc), verapamil/diltiazem, Doxazosin, Diuretic, Statin, Nitrate, Anti-platelet agents (aspirin, clopidogrel), Angiotensin converting enzyme inhibitors (ACE inhibitors), Angiotensin II Receptor Blockers (ARBs), Warfarin, SGLT2 inhibitor, Dabigatran or Apixaban, Any other anticoagulation established pre-operatively (LMWH), Metformin, Insulin.

Analysis software

All analyses will be conducted in Stata Version 14 (StataCorp. 2015. *Stata Statistical Software: Release 14*. College Station, TX: StataCorp LP).

Analysis of primary outcome

Primary analysis

The primary outcome will be the coefficient of variation of systolic blood pressure over the first 24h from start of mechanical thrombectomy. The primary exposures will be analysed by construction of a single categorical variable consisting of active versus sham stimulation.

When participants are randomised according to incorrect baseline information, under the ITT principle they should be analysed in their allocated treatment group, irrespective of the fact that their allocation was based on incorrect information. The incorrect baseline information should be kept in the randomisation record, as this reflects how the randomisation was performed, and the correct information documented for use in an adjusted analysis [7].

Analysis of secondary outcomes

- Blood pressure variability in the first 24h after mechanical thrombectomy (standard deviation, average real variability, successive variation and residual standard deviation).

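### The SAP's only sensitivity analysis for missing primary outcomes cannot be run as written: it names a group that does not exist and gives a yes/no condition in place of CV values

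*SAP*

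**What the plan says.** Protocol 14.6 commits the trial to a check: "Sensitivity analyses to assess the robustness of study results if there are missing primary outcome data will be undertaken". It gives no method, and the same section says "Any missing data will not be inputed".

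The SAP supplies the only method, in section 4 under Sensitivity analysis. It starts from the patients who leave early: "For patients discharged before the repeat stimulation intervention or repatriated to referring centres before the repeat intervention, we will undertake a sensitivity analysis". The rule follows: "The primary analysis will be repeated once assuming that all patients in the continue group with missing outcomes did not have BPV >20". The analysis is then to be repeated with the assumptions reversed, and the SAP says of the pair: "This will then give the absolute range of how much the results could change if the data were complete". It also presents this as the check on data missing not at random.

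Elsewhere the SAP describes the quantities that the rule would act on. The comparison is between two arms: "The primary exposures will be analysed by construction of a single categorical variable consisting of active versus sham stimulation". The primary outcome is blood pressure variability "as reflected by the coefficient of variation of systolic blood pressure", defined in Appendix 1 as SD divided by mean, times 100, with no cut-off. Under Exposure variables, the second session is given "provided the patient remains in Royal London Hospital".

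**The concern.** Four things that the rule needs are absent.

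- **The group.** 'Continue' matches neither arm, and the term is used nowhere else in either document.
- **The value.** The condition sorts patients into two classes, but the outcome is a number. A patient assumed to be 'not >20' could have any CV up to 20, and one assumed to be '>20' has no upper limit.
- **The other arm.** Only one group is mentioned, and the reversed assumptions are not spelled out.
- **The scale.** BPV is most naturally read as the CV in percent, but the sentence does not say so.

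The SAP's stated remit is to avoid decisions driven by the data. If outcomes are missing, the arm, the value and the direction would all have to be chosen after the pattern of missing data is known. The analysis that the protocol promises, and the SAP's only missing-not-at-random check, would then not be pre-specified.

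**Working it through.** **1. What the primary analysis is.** Inputs from the SAP's sample size calculation: CV 15 v 10, SD 4, 90% power, 5% level, 5% non-compliance in each group. The SAP's general principles call for a two-sided p-value. Treat non-compliance as dilution of the effect: 5 × (1 − 0.05 − 0.05) = 4.5. An exact two-sample t-test with SD 4 has power 0.889 at 17 per arm and 0.906 at 18 per arm. So 18 × 2 = 36, which is the plan's figure. The trial is therefore sized as a difference in mean CV, and repeating the primary analysis requires a CV for every filled-in patient.

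**2. Illustration of what the rule leaves open.** Assumptions: 18 per arm; observed CVs have the planning means and SD 4; m outcomes are missing in an arm and each is set to v (subscript s for sham, a for active).

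Difference (sham − active) = [(18 − m_s) × 15 + m_s × v_s]/18 − [(18 − m_a) × 10 + m_a × v_a]/18

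The complete-case difference is 15 − 10 = 5.0.

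*'Continue' read as active, two active missing:* 15 − (160 + 2v_a)/18

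| v_a | Condition met | Difference |
|---|---|---|
| 0 | not >20 | 6.11 |
| 15 | not >20 | 4.44 |
| 20 | not >20 | 3.89 |
| 20.1 | >20 | 3.88 |
| 25 | >20 | 3.33 |
| 30 | >20 | 2.78 |
| 40 | >20 | 1.67 |

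*'Continue' read as sham, two sham missing:* (240 + 2v_s)/18 − 10

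| v_s | Condition met | Difference |
|---|---|---|
| 0 | not >20 | 3.33 |
| 18 | not >20 | 5.33 |
| 20 | not >20 | 5.56 |
| 25 | >20 | 6.11 |

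Each condition allows a continuum of answers, and '>20' is unbounded. Under the active reading 'not >20' always gives a larger difference than '>20'; under the sham reading it always gives a smaller one. Which repeat is the favourable one therefore depends on an arm that the SAP does not name.

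**3. Five outcomes missing.** Protocol 13.1 allows for dropout of 5 patients. Take 2 sham and 3 active, with illustrative values 5 and 25.

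- Unfavourable: (240 + 10)/18 − (150 + 75)/18 = 25/18 = 1.39.
- Favourable: (240 + 50)/18 − (150 + 15)/18 = 125/18 = 6.94.

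**4. p-values.** These assume an equal-variance t-test on 34 df. Protocol 14.3 names repeated measures ANOVA, and the SAP's Primary analysis section names no test. With two active values filled in, p is 0.015 at 20.1, 0.062 at 25 and 0.17 at 30. Part of this change comes from the filled-in values inflating the pooled SD, which rises from 4.0 to 5.2 at 25. With the SD held at 4, p at 25 is 0.017.

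**5. Can the sentence be rescued by dichotomising at 20?** With normal CVs at the planning values, P(CV > 20) is 10.6% in sham (1.9 of 18) and 0.6% in active (0.1 of 18). That would be a different and sparse endpoint, not a repeat of the primary analysis, and the arm would still have to be guessed.

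**The case against.** The best defence is that the rule may hardly matter. The main analysis does not use it. Protocol 14.6 expects minimal missing blood pressure data because readings come from the routine electronic record, and the trial is a 36-patient pilot that will itself assess data completeness. If no primary outcome is missing, the rule never operates. All of this stands, and it keeps the point low in priority. It does not make the rule workable.

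Several stronger readings are tempting, and the documents do not support them.

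- *That 'not >20' must help the device if 'continue' means active, and hurt it if it means sham.* This is true only relative to the '>20' repeat. Against the complete-case 5.0 it can go either way: two active CVs at 15 give 4.44, and two sham CVs at 18 give 5.33.
- *That fewer than 2 of 36 outcomes will be missing, from the withdrawal rate below 5% in Protocol 13.3.* Withdrawal is not a missing outcome: Protocol 7.0 retains data already collected. The allowance of 5 dropouts in Protocol 13.1 is the more relevant planning figure.
- *That early leavers have no outcome.* They have already had readings during thrombectomy, Protocol Appendix A sets no number of measurements, and Protocol 14.2 and the SAP include everyone with available data. Most would have a CV from a shortened record. The tables above fill in wholly missing CVs and do not model that situation.
- *That two missing outcomes would overturn the result.* With sham complete, p reaches 0.05 only if both missing active CVs are about 24.2, which is (24.2 − 10)/4, or about 3.5 planning SDs above the active mean.

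**Conclusion.** The sensitivity analysis is wrong as written. The group, the value and the other arm's assumption are undefined, so neither the absolute range nor the missing-not-at-random check exists in usable form, and no other passage supplies them.

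The size depends on how many outcomes are missing. In the illustrations the difference moves from 5.0 to anywhere below about 3.9 with two active CVs missing and '>20' assumed. With five missing and values of 5 and 25 it spans 1.4 to 6.9. The missing counts, their split between arms and the filled-in values are all assumptions. The p-values rest further on an assumed t-test and should not carry the argument.

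A reader might infer that the primary result or the sample size is undermined. Neither is: the defect is confined to a robustness check. It should be fixed, at low priority.

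**What to change.** Before unblinding, and as a dated entry in the SAP revision history (Protocol 14.7):

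1. Replace the sentence with a rule on the CV scale that names both arms. For randomised patients with no primary outcome, repeat the primary analysis with a stated low CV in sham and a stated high CV in active, then with the two reversed. Justify both values in advance; the 5 and 25 used above are only illustrative. A delta or tipping-point analysis is an acceptable alternative.
2. Report the shift in the mean difference as well as the p-value, because extreme filled-in values also inflate the SD.
3. Name this analysis as the exception to the no-imputation statement in Protocol 14.6, which continues to govern the main analysis.
4. For patients discharged or repatriated early, keep the observed CV in the main analysis and add a sensitivity analysis for shortened records, for example by repeating the analysis without those patients. A minimum record length is not advised: it would turn observed outcomes into missing ones, contrary to Protocol 14.2, Protocol Appendix A and the SAP's analysis principles.

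The cost is a paragraph of SAP text, a few lines of Stata and a justification for the chosen values. The range will be wide if several outcomes are missing.

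Separate erratum: in SAP Appendix 1, both missing-data rules for the 7-day status outcome refer to 30-day status. Follow-up ends at day seven (Protocol 6.8), so both should read 7-day.
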